5.10.3.4. Procedural Data Collection

The following data *related to the procedure* will be collected:

- Date of procedure
- Pre-procedural imaging per hospital's standard of care, if performed at procedure visit*

**LUMINIZE_CLINICAL PROTOCOL**Document ID: VER-DOC-527
Controlled Document: VER-SIGN-3084TEMPLATE:
ONEPROJECTS/SIGN-267

Version: 4.0

Project: VERAFEYE (VER)
Date: 22-Nov-2024 14:16:10
Page: 27 / 51

- Intra-procedural imaging per hospital's standard of care, as applicable
- Identification of all investigational study devices
- Identification of non-study devices
- Rhythm at the beginning of the procedure (by means of a 12-lead ECG)
- Method of delivering sedation or anesthesia for the procedure
- Method of access to left atrium: single or double transseptal
- Performance of the study device
- Procedural outcome details
 - Ablation procedures: successful isolation of CTI (typical AFL) or PVs (AF)
 - LAA/ASD closure procedures: successful deployment of closure device

At the end of the procedure, the following information will be collected:

- Total procedure time, defined as time elapsed from time first access sheath insertion into the subject until the last catheter removed
- Total fluoroscopy time and dose
- Total time VERAFEYE imaging catheter was in the body, defined as time elapsed from inserting the VIC into the subject until the time of VIC removal from the subject
- Rhythm at end of case (by means of a 12-lead ECG)
- Physical assessment
- Concomitant procedures, if applicable
- Changes in Medication Regimen
- Adverse Events if applicable
- Device Deficiencies
- Protocol Deviations, if applicable
- The data collected through the System Console will be saved and stored to external media, as provided by the sponsor

*Standard of care imaging data will be saved and stored to external media, as provided by the sponsor

After the completion of the procedure, the images collected with the VERAFEYE System during the procedure may be reviewed with the physician and the physician will be asked to rate the performance of the system by means of a questionnaire.

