5.5. STUDY OBJECTIVE

The objective of the study is to collect data on the usability and integration of the VERAFEYE System in standard of care

- catheter-based ablation treatments for Typical Atrial Flutter (AFL) or Atrial Fibrillation (AF)
- left atrial appendage closure (LAAC) procedures
- atrial septal defect (ASD) closure procedures

Results from this study will be used to guide development and refinement the VERAFEYE System.

**LUMINIZE_CLINICAL PROTOCOL**Document ID: VER-DOC-527
Controlled Document: VER-SIGN-3084TEMPLATE:
ONEPROJECTS/SIGN-267

Version: 4.0

Project: VERAFEYE (VER)
Date: 22-Nov-2024 14:16:10
Page: 17 / 51**5.6. STUDY ENDPOINTS**

This is a feasibility study and no formal endpoints or hypothesis testing are planned in the study. The study is not designed to collect data for product approval and as such does not have a safety or efficacy endpoint.

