5.7. STUDY DESIGN

This is a prospective, non-randomized, single-arm feasibility study. This study is a pilot stage study according to ISO/FDIS 14155: 2020 (E) - Annex I. Results from this study will be used to guide development and refinement of the VERAFEYE System.

The study is designed to assess the usability and integration of the VERAFEYE System in standard of care, catheter-based ablation treatments for Typical Atrial Flutter (AFL) or Atrial Fibrillation (AF), standard of care left atrial appendage closure (LAAC) procedures and standard of care atrial septal defect (ASD) closure procedures. Results from this study will be used to guide development and refinement the VERAFEYE System.

Intended Users of the VERAFEYE System are interventional cardiologists and electrophysiologists who are trained in percutaneous and transseptal procedures and who have completed the VERAFEYE System training. The VERAFEYE System training is offered by the Sponsor. The VERAFEYE System should only be performed by these Intended Users.

A prospective study design will ensure that identical procedures are followed for data capture and review.

Up to 4 operators per site will be allowed to perform study procedures, unless written approval from LUMA Vision was obtained.

A sample size of 40 subjects was chosen to allow for sufficient feasibility testing and data collection for the ablation, LAA and ASD closure procedures. The sample size is not statistically based but is based on a reasonable number of data sets to assess the images collected with the VERAFEYE System.

In protocol rev 4.0, the sample size was extended from 20 subjects to 40 subjects, in order to collect more clinical data for further system development and to ensure the collection of information from different operators.

Enrolment in this study is competitive, there is no limit of enrolments per site.

Subject procedures will follow a sequential pattern (one site after the other) to allow LUMA Vision field support personnel to be present during the procedures and to ensure the availability and installation of necessary equipment.

[figure not shown]
Enrolment in the study is expected to be completed in approximately 6 months. The follow-up for each participant is expected to be approximately 7 days, therefore the total study duration is expected to last approximately 7 months.

**LUMINIZE_CLINICAL PROTOCOL**Document ID: VER-DOC-527
Controlled Document: VER-SIGN-3084TEMPLATE:
ONEPROJECTS/SIGN-267

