**LUMINIZE_CLINICAL PROTOCOL**

Document ID: VER-DOC-527
Controlled Document: VER-SIGN-3084

Study enrolment will be considered as complete when 40 procedure subjects have been enrolled (see section 'subject classification').

Enrolment in the study is expected to be completed in approximately 6 months. The follow-up for each participant is expected to be approximately 7 days, therefore the total study duration is expected to last approximately 7 months.

Up to 2 sites in Ireland may participate in the study. Enrolment in this study is competitive, there is no limit of enrolments per site.

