5.9.2. SUBJECT CLASSIFICATION

- Enrolled subject- Any participant who signs the informed consent form.
- Screen Failure subject- Any participant who signs the consent form but is found to not meet eligibility criteria.
- Intent subject- Any participant who signs the consent form, met the eligibility criteria but did not have the VERAFEYE Imaging Catheter inserted into the body.
- Attempt subject- Any participant who signs the consent form, met the eligibility criteria, did have the VERAFEYE Imaging Catheter inserted into the body but did not undergo the ablation/LAA/ASD closure procedure per this study protocol.
- Procedure subject - Any participant who undergoes the ablation/LAA/ASD closure procedure with the VERAFEYE System as imaging system per this study protocol.

These subjects are followed in accordance with the Follow-Up schedule and data will be included in all study analyses.

[figure not shown]
- Withdrawn subject - A participant who chooses to or is withdrawn from the study.
- Lost-to-follow up subject - A participant who cannot be reached anymore after 3 attempts.

Enrolment will be considered as complete when 20 procedure subjects have been enrolled.

The Figure below shows the subject classifications.

**LUMINIZE_CLINICAL PROTOCOL**Document ID: VER-DOC-527
Controlled Document: VER-SIGN-3084TEMPLATE:
ONEPROJECTS/SIGN-267

Version: 4.0

Project: VERAFYE (VER)
Date: 22-Nov-2024 14:16:10
Page: 22 / 51**Figure 5: Subject Classifications****5.9.3. END OF STUDY**

Individual study subject participation will end when the last subject follow-up visit is completed; when the subject withdrew or was withdrawn from the study or when the subject is considered as lost-to-follow up.

The study will be considered as complete when the last subject's follow up visit occurs or when subjects are no longer being considered for participation. Routine management and standard practice of care will continue for the subjects who have completed the study.

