5.10.3.2. VERAFEYE System Preparation/LUMA Vision Support

The System Console will create a record for each view attempted. In order to accurately capture information

relevant to the study, the following steps need to be followed for each procedure:

1. Start a new study. Input subject name, date of birth, gender and subject ID
2. In Graphical User Interface (GUI) main screen, select appropriate 2D and 4D configs.
3. In the Component screen,
 - Home the motor (if the button is enabled).
 - Input the VERAFEYE Imaging Catheter serial number with the format.
 - Confirm the VERAFEYE Imaging Catheter has been flushed and confirm the connection.
4. If tracking sensors are disconnected,
 - Disable tracking from the tracking tab before inserting the sensor to the control unit.
 - Enable tracking again after connecting the sensor.
5. Start imaging.
6. Navigate to intended view (see section 12.6), manipulating 3D volume and 2D plane as required.
7. Acquire clip and full data.
8. Freeze if needed for measurements / change configurations and repeat acquisition.
9. Navigate to the next intended view (see section 12.6).

**LUMINIZE_CLINICAL PROTOCOL**Document ID: VER-DOC-527
Controlled Document: VER-SIGN-3084TEMPLATE:
ONEPROJECTS/SIGN-267

Version: 4.0

Project: VERAFEYE (VER)
Date: 22-Nov-2024 14:16:10
Page: 25 / 51

10. Before finishing a study, always freeze the imaging and wait until the motor stops. Then, select the "finish" option in the dropdown with the subject name. Close the study and the data will automatically save.

LUMA Vision will ensure (a) company representative(s) is/are present during each procedure to manage the System Console and to assist the physician with the VERAFEYE Imaging Catheter preparation.

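### Do the unstated order of image review and operator rating, and the silence on attempt subjects, spoil the usability ratings?

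*Combined protocol and SAP*

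**What the plan says.** Section 5.10.3.4 holds the only text on the questionnaire. After the procedure is complete, the images "may be reviewed with the physician and the physician will be asked to rate the performance of the system by means of a questionnaire". The lists in that section also include an item on how the study device performed and an item for device deficiencies. Neither list has an item for whether an image review took place.

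The rating serves the objective in section 5.5, which is to "collect data on the usability and integration of the VERAFEYE System". Section 5.6 adds that "no formal endpoints or hypothesis testing are planned in the study", and section 5.12 limits the analysis to descriptive methods.

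On the setting, section 5.10.3.2 states: "LUMA Vision will ensure (a) company representative(s) is/are present during each procedure to manage the System Console". Section 5.14.3 lists a look back at equipment performance after the case among the typical tasks of sponsor staff. Section 5.7 says: "A prospective study design will ensure that identical procedures are followed for data capture and review".

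On who is covered, section 5.9.2 defines an attempt subject as an eligible, consented participant who "did have the VERAFEYE Imaging Catheter inserted into the body but did not undergo the ablation/LAA/ASD closure procedure per this study protocol". After the definition of a procedure subject comes the sentence: "These subjects are followed in accordance with the Follow-Up schedule and data will be included in all study analyses". Section 5.9.1 sets the target: "Study enrolment will be considered as complete when 40 procedure subjects have been enrolled".

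**The concern.** Two conditions of rating are allowed. One operator may score the system straight after the case. Another may first go through the images, perhaps with a sponsor representative who was in the room. If the order and the attendance are not recorded, a summary of the ratings could mix the two, and a reader could not tell. That sits awkwardly beside the sentence in section 5.7 on uniform data capture.

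The second worry is about attempt subjects. Sections 5.10.4 and 5.10.5 each say that they apply to attempt and procedure subjects. Section 5.10.3.4 has no such line, and it ties the rating to the end of the procedure. A case in which the catheter went in but the procedure was not done might say a good deal about usability, and it might go unrated.

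At stake is how far the descriptive ratings can be taken at face value on the study's only stated objective.

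**Working it through.** The plan gives no rating scale, summary statistic or expected value for the questionnaire, so there is no figure of its own to reproduce. The check has three parts.

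**1. Effect of an image review.** Let m0 be the mean rating without a prior review, d the change a review brings, and p the share of ratings that follow one. Then

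pooled mean = m0 + p × d, with p between 0 and 1.

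The shift lies between 0 and d. The documents give neither d nor p, nor the sign of d. The formula describes how a mixture works and is no evidence of bias.

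**2. Leaving out attempt subjects.** Enrolment runs to 40 procedure subjects (synopsis and sections 5.7 and 5.9.1; one line in section 5.9.2 still reads 20, a leftover from before the increase). Attempt subjects come on top. Let a be their number, which the documents do not give and which is assumed here. Let P be the share rated favourably among procedure subjects and Q the share among attempt subjects.

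- Unrated share of catheter-inserted cases = a/(40 + a)
- Overstatement of the favourable share = [a/(40 + a)] × (P − Q)

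| a (assumed) | a/(40 + a) | Favourable share over all cases if P = 1, Q = 0 |
|---|---|---|
| 1 | 1/41 = 2.4% | 40/41 = 97.6% |
| 2 | 2/42 = 4.8% | 40/42 = 95.2% |
| 4 | 4/44 = 9.1% | 40/44 = 90.9% |

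The middle column is the ceiling, reached only at P = 1 and Q = 0. If Q equals P there is no overstatement, and if Q exceeds P the share is understated. For scale, one procedure subject changing category moves the share by 1/40 = 2.5 points, slightly more than the ceiling for a = 1.

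**3. What the rest of the protocol already supplies.**

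- *Attempt cases.* Table 6 (section 5.13.1) counts inadequate usability or performance, and use errors, as device deficiencies. Section 5.13.1 makes all of them reportable, section 5.13.2 applies from enrolment, and Table 7 sets 3 calendar days. An attempt case that failed because of the device should leave a usability record. Only the questionnaire score might be missing.
- *Scope lines.* Sections 5.10.4 and 5.10.5 concern visits that intent subjects and screen failures do not have, so they need to say whom they cover. Attempt subjects do reach the procedure visit that section 5.10.3.4 describes. The sentence in section 5.9.2 on analyses includes data and excludes nobody by its terms.
- *Recording.* The rating is something the protocol asks for, so it fits the purpose of the Technical Source Form (section 5.15.3). Table 9 is introduced as not exhaustive. The questionnaire, the case report forms and the data management plan (section 5.15.1) are not among the documents and may cover order and attendance.
- *Sponsor presence.* A representative attends every procedure, so contact with the sponsor is common to all cases. Section 5.14.3 does not link the look back at equipment performance to the image review or to the rating.
- *Order.* Section 5.10.3.3 says the treatment is not guided by VERAFEYE data, and section 5.7 bases the sample size on assessing the images. Asking for the rating once the images have been seen is a reasonable choice, and it is the natural reading of the sentence.

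**The case for a change.** The best case for acting is this. Even if the review is read as coming first, its being optional leaves some ratings with it and some without. An optional step need not be logged on a form meant for required items. Sponsor staff are on hand, and the treatment is not guided by the device, so a later look at the images could change what the operator is rating. A descriptive study depends on readers knowing what was measured and when, and section 5.7 gives different operators as one reason for raising the sample to 40. Order that was not recorded may not be recoverable. A few extra fields would cost little.

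Much of this stands as description: the order, the attendance, the recording of the review and the scope are not stated. The step from there to harm does not. Nothing says the ratings will be averaged or pooled. Attendance of the sponsor at the review is a guess. No review effect is shown, and the percentages rest on assumed counts at an extreme.

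Requiring the rating before the review would give every case one common condition. It would also collect the main rating before the operator has gone back over the images, call for a second rating, and divide about 40 cases into several groups, all through an amendment needing ethics approval (section 5.14.9). That is a trade-off and not a clear gain. Noting order and attendance is a matter for the forms and can be settled there.

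**Conclusion.** No change to the plan follows. Section 5.10.3.4 leaves real gaps, but they are details of a questionnaire and source forms that are not among the documents, and those preparing the forms and the report can fill them sensibly. They can note whether a review came before the rating and who attended, and list any attempt subjects separately.

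No endpoint, test or planned comparison depends on the ratings, and the descriptive conclusion would stand if the plan were followed as written. The effect of a review cannot be sized from the documents. The effect of leaving out attempt subjects is at most 2.4 to 9.1 percentage points for one to four such subjects. That range assumes those counts, a favourable/unfavourable summary the plan does not specify, and ratings wholly favourable in one group and wholly unfavourable in the other.

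Confidence is moderate, because the forms themselves could not be examined.

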5.10.4. POST-PROCEDURE VISIT

The Post-Procedure visit is applicable for attempt subjects and procedure subjects.

The post-procedure visit will occur per standard of care but not to exceed 2 days from the end of the study procedure. The data collection requirements of the post procedure visit are outlined below:

- Date of visit
- Physical assessment (incl. vital signs and 12-lead ECG)
- Changes in Medications Regimen

**LUMINIZE_CLINICAL PROTOCOL**Document ID: VER-DOC-527
Controlled Document: VER-SIGN-3084TEMPLATE:
ONEPROJECTS/SIGN-267

Version: 4.0

Project: VERAFYE (VER)
Date: 22-Nov-2024 14:16:10
Page: 28 / 51

- Adverse Events, if applicable
- Protocol Deviations, if applicable

5.10.5. 7-DAY FOLLOW-UP

The 7-day follow-up is applicable for attempt subjects and procedure subjects.

If the patient was discharged prior to the day 7 follow-up, a telephone contact will occur. If the patient is still hospitalized at the time of the day 7 follow-up, the 7 days follow-up will be performed as an in-hospital visit. The data collection at the day 7 follow-up includes:

- Date of contact (visit/telephone call)
- Changes in Medication Regimen
- Adverse Events, if applicable
- Protocol Deviations, if applicable

5.10.6. DATA COLLECTION SCHEDULE

The data collection schedule for the study is shown in Table 3.

Table 3: Data Collection Schedule

Procedure/Assessment	Baseline Visit	Procedure Visit	Post-Procedure Visit	7- Days Follow-Up (office/phone call)
	≤ 60 days prior Day 0	Day 0	Day 0- Day 2	Day 7
Informed Consent Form and Process	X			
Eligibility Criteria	X			
Demographics including age and gender	X			

**LUMINIZE_CLINICAL PROTOCOL**Document ID: VER-DOC-527
Controlled Document: VER-SIGN-3084TEMPLATE:
ONEPROJECTS/SIGN-267

Version: 4.0

Project: VERAFEYE (VER)
Date: 22-Nov-2024 14:16:10
Page: 29 / 51

Procedure/Assessment	Baseline Visit	Procedure Visit	Post-Procedure Visit	7- Days Follow-Up (office/phone call)
Medical history	X			
Physical Assessment	X	X	X	
Cardiac imaging	X		(X)	(X)
Medication regimen	X	X	X	X
Procedural data collection		X		
Investigational Data Collection		X		
Protocol Deviations	X	X	X	X
Adverse Events	X	X	X	X
Device Deficiencies		X		

*: per hospital standard of care

(): optional, collect only if performed per hospital's standard of care

5.11. POTENTIAL RISKS AND BENEFITS**5.11.1. RISKS ASSOCIATED WITH THE PROCEDURE**

There are risks associated with the standard procedures that are part of the study such as exposure to radiation (e.g. because of the usage of fluoroscopy, or because of the standard of care imaging modality performed prior to/during the ablation or LAA/ASD closure procedures) or risks that are common to ablation or LAA/ASD closure procedures. These risks are not changed by the use of the VERAFEYE System.

5.11.2. RISKS ASSOCIATED WITH THE STUDY DEVICE

The risks associated with use of the VERAFYE System are not substantially or incrementally different from commercially available and widely used ICE systems for cardiac EP or LAA/ASD closure procedures. The below list of potential adverse effects associated with the use of this device and other devices in this field is widely known and understood when considering usage of ICE in EP or LAA/ASD closure procedures.

5.11.3. POTENTIAL ADVERSE EVENTS

Subjects participating in this study are subject to the same risks shared by all patients undergoing an ablation procedure for treatment of AFL or AF; or an LAA/ASD closure procedure.

Based upon the current literature, the tables below includes an alphabetical list of the possible anticipated adverse events and possible adverse device effects associated with ablation catheters and closure devices. Occurrence of any of the listed events could lead to prolonged hospitalization for the subject.

Table 4: Potential adverse events during catheter ablation procedures

Access site complications	Headache
Allergic reaction	Heart failure
Anemia	Hematoma
Arrhythmias	Hemothorax
Bleeding/Hemorrhage	Hemodynamic instability
Blurred vision	Hypertension/Hypotension
Cardiac perforation	Inadvertent injury to adjacent structures
Cardiac/pulmonary arrest	Infection
Catheter entrapment	Myocardial infarction
Cerebrovascular accident (CVA)	Nerve weakness/palsy/injury (i.e. phrenic/ vagus)
Chest discomfort/pain or pressure	Pericarditis
Complete heart block (transient/permanent)	Pneumothorax

**LUMINIZE_CLINICAL PROTOCOL**Document ID: VER-DOC-527
Controlled Document: VER-SIGN-3084TEMPLATE:
ONEPROJECTS/SIGN-267

Version: 4.0

Project: VERAFYE (VER)
Date: 22-Nov-2024 14:16:10
Page: 31 / 51

Complications of sedative agents/anesthesia/medications	Pseudoaneurysm
Coronary artery spasm	Pulmonary complications (i.e. edema, pulmonary hypertension, pleuritis, pneumonia)
Cough	Pulmonary vein stenosis
Death	Radiation injury/exposure
Diaphragmatic paralysis	Renal insufficiency/failure
Dizziness or lightheadedness	Respiratory Depression
Edema	Residual atrial septal defect (ASD)
Pericardial effusion/pleural effusion	Skin burns (i.e. radiation/defibrillator/ cardioverter)
Elevated cardiac enzymes	ST segment Elevation
Embolism (venous/arterial) (i.e. air, gas, thrombo, pulmonary)	Sore Throat
Endocarditis	Tamponade
Esophageal injury	Thrombus/thrombosis
Fever	Transient ischemic attack (TIA)
Exacerbation of existing conditions	Valvular damage
Fatigue	Vasospasm
Fistula (arterial-venous, atrial-esophageal)	Visual disturbances
Gastroparesis	Vasovagal reactions

Table 5: Potential adverse events during catheter closure procedures

Air embolism	Hemoptysis
--------------	------------

**LUMINIZE_CLINICAL_PROTOCOL**Document ID: VER-DOC-527
Controlled Document: VER-SIGN-3084TEMPLATE:
ONEPROJECTS/SIGN-267

Version: 4.0

Project: VERAFYE (VER)
Date: 22-Nov-2024 14:16:10
Page: 32 / 51

Airway trauma	Hypotension
Allergic reaction to contrast media/medications or device	Hypoxia
Altered mental status	Improper wound healing
Anemia requiring transfusion	Inability to reposition, recapture, or retrieve the device
Anesthesia risks	Infection/pneumonia
Angina	Interatrial septum thrombus
Anoxic encephalopathy	Intratracheal bleeding
Arrhythmias	Major bleeding requiring transfusion
Atrial septal defect	Misplacement of the device / improper seal of the appendage / movement of device from appendage wall
AV fistula	Myocardial erosion
Bruising, hematoma or seroma	Nausea
Cardiac perforation	Oral bleeding
Chest pain/discomfort	Pericardial effusion / tamponade
Confusion post procedure	Pericarditis
Congestive heart failure	Pleural effusion
Contrast related nephropathy	Prolonged bleeding from a laceration
Cranial bleed	Pseudoaneurysm
Death	Pulmonary edema
Decreased hemoglobin	Pulmonary embolism

**LUMINIZE_CLINICAL PROTOCOL**Document ID: VER-DOC-527
Controlled Document: VER-SIGN-3084TEMPLATE:
ONEPROJECTS/SIGN-267

Version: 4.0

Project: VERAFEYE (VER)
Date: 22-Nov-2024 14:16:10
Page: 33 / 51

Deep vein thrombosis	Renal failure
Device embolism/migration	Respiratory insufficiency / failure
Device fracture	Surgical removal of the device
Device thrombosis	Systemic embolism
Edema	TEE complications (throat pain, bleeding, esophageal trauma)
Bleeding	Thrombocytopenia
Fever	Thrombosis
Groin pain	Transient ischemic attack (TIA)
Groin puncture bleed	Valvular damage
Hematuria	Vasovagal reactions

